# **The Role of Fatty Acids in Vaccine Efficacy: A Randomized Controlled Clinical Trial**

## **1. Background**

Rabies is an acute zoonotic infectious disease caused by central nervous system invasion by rabies virus. At present, there is still a lack of effective treatment, and once clinical symptoms appear, it is almost 100% fatal. Human rabies is a 100% vaccine-preventable disease, yet it continues to kill. Rabies vaccination within 24 hours of exposure may reduce the incidence of rabies. The efficacy of rabies vaccination is crucial to avert deaths. Pre-exposure prophylaxis is also effective, and the current recommended pre-exposure vaccination program in China is: 0 days, 7 days, 21 days.

The health of the human body is inseparable from various nutrients. There are studies suggesting that arachidonic acid (ARA) has an immunomodulatory effect, has potential ability to promote efficacy of certain vaccination, but there is limited evidence for its effect on rabies vaccines. Therefore, this study will explore the effects of nutritional supplements on the effectiveness of rabies vaccination.

## **2. Study design**

This study intends to use a randomized controlled trial design to vaccinate all participants against rabies and perform ARA interventions during vaccination.

## **3. Study objectives:**

The objectives of this study are:

- 1) to test the ARA intervention on promoting rabies vaccination efficacy;
- 2) to evaluate the safety of using ARA intervention;
- 3) to explore the potential mechanism

## **4. Methods**

### **4.1 Participants**

### **Inclusion criteria**

- 1) 18-45 years old;
- 2) BMI 18.5-24.9 kg/m^2;
- 3) Have not received rabies vaccination.

### **Exclusion criteria**

- 1) Those who have severe disorders of abnormal lipid metabolism;
- 2) Those who have used lipid-lowering drugs, weight loss drugs, and insulin drugs in the past three months;
- 3) Those who have received other vaccines in the past three months;
- 4) Those who have used probiotics or prebiotics in the past three months;
- 5) Those who have used steroids and immunosuppressants, other hormonal drugs in the past year;
- 6) Those with immunodeficiency diseases;
- 7) Those with a history of severe vaccine allergies;
- 8) Those who have disorders of liver and kidney metabolism;
- 9) Those who have had fever, cold, severe diarrhea and other diseases in the past month.
- 10) Smokers in the last year.

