### **Drop out**

- 1) Use of other nutritional supplements during the intervention;
- 2) Those who do not consume nutritional supplements as prescribed by the doctor
- 3) Those who develop a major illness;
- 4) Those who experience severe vaccine allergy;
- 5) Voluntary withdrawal.

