### **4.2 Sample size**

According to the mean and standard deviation of the two groups of neutralizing

antibody,  $1323 \pm 1093.9$  in the experimental group and  $164.8 \pm 123.4$  in the control group; using the standard deviation combined formula  $s = \sqrt{\frac{s_1^2(n_1-1)+s_2^2(n_2-1)}{n_1+n_2-2}}$ , the combined standard deviation was calculated as 778.4.

With reference to the above results, it was determined that the expected difference between the outcome indicators of the experimental and control groups in this study was 1158.2, and the standard deviation was 778.4. Taking the test level  $\alpha = 0.05$  and the degree of certainty  $1-\beta = 0.9$ , the minimum sample size for each group was calculated as 10 people according to the following formula, and setting the expected loss of follow-up rate at 20%, 13 people needed to be recruited in each group.

$$N = 2 \times \left( \frac{Z_{1-\frac{\alpha}{2}} + Z_{1-\beta}}{\delta} \right)^2 \times s^2$$

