#### **Supplements used in interventions:**

Placebo group: six ×500 mg sunflower oil capsules each day.

Day 3 ARA group: 512.4mg/day ARA via 6 × 500mg ARA capsules.

Day 6 ARA group: 512.4mg/day ARA via 6 × 500mg ARA capsules.

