## 2) Safety indicators

① Blood glucose and lipids: tested on days 3 and 13 of the test;

② Blood count: tested on day 3 and 26 of the trial;

③ Anxiety: to evaluate the mood changes after intervention with GAD-7.

tested on day 13 of the trial.

④ Adverse reaction records: allergy, gastrointestinal discomfort during the trial.

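### The only allergy exclusion is for severe vaccine allergy, so a known allergy to a capsule ingredient does not bar entry

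*Protocol*

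**What the plan says.** Section 2 of the protocol plans to "vaccinate all participants against rabies and perform ARA interventions during vaccination", so every participant receives the vaccine. Under the supplements heading in section 4.3, the comparator is given as "Placebo group: six ×500 mg sunflower oil capsules each day" and the active product as "Day 3 ARA group: 512.4mg/day ARA via 6 × 500mg ARA capsules". The Day 6 ARA arm takes the same six capsules.

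Eligibility is set out in section 4.1 as 3 inclusion and 10 exclusion items. Two of them bear on this point:

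- Inclusion 3: "Have not received rabies vaccination".
- Exclusion 7: "Those with a history of severe vaccine allergies".

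After entry, allergy appears twice more. Item 4 of the drop-out list reads "Those who experience severe vaccine allergy", and the safety indicators in section 4.4 include "Adverse reaction records: allergy, gastrointestinal discomfort during the trial".

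**The concern.** Two kinds of product are given, a vaccine and an oil capsule, but the entry criteria ask about allergy to only one of them, and then only about past severe reactions. The protocol itself regards allergy during the trial as foreseeable, because it records it as a safety indicator. A capsule allergy that the candidate already knows about could be found with one question at screening. As written, it would first come to light after the person had been randomized and had started the capsules.

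What is at stake is an avoidable exposure of a participant. Objective 2 is the safety of the ARA intervention, so it is also reasonable that entry screening should cover the product whose safety is being studied, and its comparator.

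**Working it through.** No figure in the protocol depends on this point, so the check consists of taking each kind of allergy history through the full eligibility list.

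**Which histories are stopped at entry**

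| History known at screening | Stopped by | Result |
|---|---|---|
| Reaction of any severity to an earlier rabies vaccine | Inclusion 3 (any earlier rabies dose rules the person out) | Not eligible |
| Severe allergic reaction to another vaccine | Exclusion 7 | Not eligible |
| Allergy to the ARA oil, sunflower oil or capsule shell | No item | Eligible |
| Allergy to a rabies-vaccine constituent, learned other than through a severe vaccine reaction | No item | Eligible |

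The remaining exclusions concern lipid disorders; lipid-lowering, weight-loss and insulin drugs; recent vaccination; probiotics and prebiotics; steroids, immunosuppressants and other hormonal drugs; immunodeficiency; liver and kidney disorders; recent illness; and smoking. One of these could remove an allergic person by coincidence, for example through steroid use in the past year, but none does so because of the allergy.

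**What happens after entry**

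- Drop-out item 4 is limited to severe vaccine allergy and does not reach a reaction to the capsules.
- A participant who reacts to the capsules and stops them would leave under item 2 (supplement not taken as prescribed) or item 5 (own wish), or under item 3 if the reaction counts as a major illness.
- The adverse-reaction record in section 4.4 is not limited to vaccines, so the reaction itself would still be recorded.

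**Whether a size can be given**

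The plan's only related figure is the group size in section 4.2, and it reproduces. With a difference of 1158.2, a standard deviation of 778.4, two-sided α = 0.05 and power 0.9:

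N = 2 × ((1.960 + 1.282) / 1158.2)² × 778.4² = 9.49, rounded up to 10 per group; 10 / 0.8 = 12.5, rounded up to 13.

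This calculation neither uses nor is changed by the allergy criterion. One event in an arm of 13 is 1/13 = 7.7%, and one loss is one of the 13 − 10 = 3 allowed for, but both statements hold for any single event or loss from any cause. They do not measure this gap. A real measure would need the ingredients and the frequency of allergy to them among candidates, and the protocol gives neither.

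**The case against.** The strongest reply is that vaccine allergy is already well covered at entry. This stands. A reader might infer that inclusion 3 leaves exclusion 7 with nothing to do, since candidates who have never had a rabies vaccine cannot have reacted to one. The text does not support that. Inclusion 3 keeps out anyone who reacted to an earlier rabies dose, and exclusion 7 then keeps out people with severe reactions to other vaccines, which is the vaccine-allergy history that unvaccinated candidates can have. The two criteria complement each other. Nor is vaccine allergy left until after randomization.

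Three further objections also hold:

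- A reader might take drop-out item 4 as the route by which capsule allergy removes participants. Its wording covers vaccines only.
- A reader might expect a bias in the trial's answer, for instance a sunflower-oil reaction on placebo masking an ARA signal. That needs an allergic person to be enrolled, to be allocated to placebo and to react, at the same time as a true ARA signal. The protocol gives no probability for any of these steps. For vaccine constituents, all arms receive the same vaccine, so randomization balances the risk in expectation.
- The loss allowance of 20% in section 4.2 already provides for sporadic drop-outs.

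It can also be said that this is an omission and not an error, and that an allergy question may stand on consent pages that were not available for review. That holds only in part. Entry criteria belong in the protocol, the list as shown is complete, and it does not fit the products named in section 4.3. An informal question at screening would not make an allergic candidate ineligible under the criteria as written.

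**Conclusion.** The point holds as a mismatch between the entry criteria and the products. Exclusion 7 is the only allergy criterion and covers severe vaccine allergy alone. It leaves out known allergy to either capsule, and known allergy to a vaccine constituent that was discovered in some other way. The capsule gap is the clearer of the two.

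The consequence is small: a modest gain in participant safety, at low priority. This rests on the assumption that such allergies are rare among healthy adults aged 18 to 45, which the protocol neither states nor contradicts. It also rests on every participant belonging to one of the three arms described; section 4.3 mentions four groups but describes only three. No effect on power, on the antibody comparison or on the safety contrast is shown.

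**What to change.** Reconcile exclusion 7 with the supplements in section 4.3 and the allergy record in section 4.4. Keep its present content and extend it to known allergy to any component of the study rabies vaccine, the ARA capsule or the sunflower oil capsule, including the shell. Ask this before randomization. To make the question answerable, screening staff need the ingredient lists of the vaccine and both capsules.

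The cost is one line in the exclusion list, one screening question and very few candidates lost. The sample size and the visit schedule are unaffected.

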### **Drop out**

- 1) Use of other nutritional supplements during the intervention;
- 2) Those who do not consume nutritional supplements as prescribed by the doctor
- 3) Those who develop a major illness;
- 4) Those who experience severe vaccine allergy;
- 5) Voluntary withdrawal.

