### 4.3 Randomizing

Using the random number method, the study subjects were randomized into four groups, performed on R version 4.1.3, and after 3 days of a low-volume diet of a certain nutrient, nutritional supplement intervention was performed 3 days before the first dose of vaccine to the second dose of vaccination, in which the first group will receive nutritional supplements of 500mg/day from days 3 of the study; The second group will receive nutritional supplements 500mg/day, starting on days 6 of the study; The third group will receive a placebo and days 3 of the study.

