###### **2) Secondary indicators**

- ① Serum blood fatty acid profiles: to reflect the change of fatty acid profiles after intervention. Will be tested on day 6, 13, 16 and 19.

- ② Cytokines: to test the potential blood cytokines changes triggered by ARA supplementation. Will be tested on day 6, 13, 16, 19 and 26

- ③ Feces microbiota: the microbiota in feces samples will be examined with metagenome to explore the potential gut-immune response caused by intervention. Will be tested on Day 3, 6, 13, 16, 19 and 26 of the study.

- ④ Blood metabolites: To examine the metabolites changes in blood after intervention.

Will be tested on Day 6, 13 and 16 .

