### **Biological sample collection (6 times in total):**

Test Day 3: venous fasting blood collection of 30 ml and feces of 10 g;

Trial Day 6 (vaccination Day 0): 5 ml of blood collected intravenously; 10 g of feces;

Trial Day 13 (vaccination Day 7): 5 ml of blood collected intravenously on an empty stomach; 10 g of feces;

Trial Day 16 (vaccination Day 10): 5 ml of blood collected intravenously; 10 g of feces;

Trial Day 19 (vaccination Day 13): 30 ml of blood collected intravenously; 10 g of feces;

Trial Day 26 (vaccination Day 20): 5 ml of blood collected intravenously; 10 g of feces.

Preservation of serum, plasma and whole blood: frozen at -80°C after sampling.

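### No criterion names antibiotics, and the limit on other supplements ends with dosing, while microbiota and fatty-acid sampling continues: a minor, cheap gap in the mechanism outcomes

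*Protocol*

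**What the plan says.** **Supplements on study.** The only rule on other supplements after enrolment is item 1 of the Drop out list (Protocol, 4.1): "Use of other nutritional supplements during the intervention". Section 4.3 sets the dosing window: "nutritional supplement intervention was performed 3 days before the first dose of vaccine to the second dose of vaccination".

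**Gut flora at screening.** Exclusion item 4 (Protocol, 4.1) removes "Those who have used probiotics or prebiotics in the past three months". No inclusion, exclusion or drop-out item mentions antibiotics. The nearest cover is exclusion item 9, which looks back one month for recent illness, and drop-out item 3, which concerns major illness on study.

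**Outcomes exposed.** Under Secondary indicators (Protocol, 4.4), serum fatty acids are measured "to reflect the change of fatty acid profiles after intervention. Will be tested on day 6, 13, 16 and 19". The fecal metagenome is meant "to explore the potential gut-immune response caused by intervention", and the schedule reads "Will be tested on Day 3, 6, 13, 16, 19 and 26 of the study". Both serve the third study objective, "to explore the potential mechanism".

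**The concern.** The conduct rules do not fully match the outcomes they appear meant to protect.

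(a) A three-month look-back for probiotics and prebiotics makes sense only as protection of the gut flora. Antibiotics also disturb the flora, and someone who finished a course six weeks before enrolment meets every stated criterion. Recovery of the flora after that course could then overlap with the six fecal samples.

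(b) A participant who starts a fatty-acid product, a probiotic or a prebiotic after dosing ends breaks no stated rule, although several outcomes are still being sampled.

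At stake is the precision of the fatty-acid and microbiota comparisons in small arms. These are eligibility and conduct rules, so an analysis plan cannot supply them later.

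**Working it through.** **Step 1: when the supplement rule ends.** The Protocol gives no date for the second dose. The Background cites a schedule of vaccination days 0, 7 and 21. The sample calendar puts vaccination Day 0 at trial Day 6 and contains the entry "Trial Day 13 (vaccination Day 7". Second dose = 6 + 7 = trial Day 13. This is an inference, but these sections support it. The last sample, trial Day 26, is vaccination Day 20, one day before a third dose on that schedule, which fits.

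**Step 2: samples after Day 13** (days from Primary and Secondary indicators).

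| Outcome | All days | After Day 13 | Longest gap |
|---|---|---|---|
| Fatty acids | 6, 13, 16, 19 | 2 of 4 | 19 − 13 = 6 days |
| Metabolites | 6, 13, 16 | 1 of 3 | 16 − 13 = 3 days |
| Feces | 3, 6, 13, 16, 19, 26 | 3 of 6 | 26 − 13 = 13 days |
| Cytokines, antibodies | 6, 13, 16, 19, 26 | 3 of 5 | 26 − 13 = 13 days |

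**Step 3: antibiotic cover.** Exclusion item 9 reaches back one month and acts only through illness. What remains uncovered is use between one and three months before enrolment, and any course given without an excluded illness.

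**Step 4: arm sizes.** The plan's own figures reproduce: N = 2 × ((1.960 + 1.282) / 1158.2)² × 778.4² = 9.49, rounded up to 10; 10 / (1 − 0.20) = 12.5, rounded up to 13. This point does not change them.

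**Step 5: effect of one user.** The Protocol gives neither a use rate nor the effect of use, so all rates and shifts from here on are assumptions. If one participant in one arm is shifted by k SD, the arm mean moves by k·SD/n, and the SE of the difference is SD·√(2/n). The contrast therefore moves by k/√(2n) SE.

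| k | n = 10 | n = 13 |
|---|---|---|
| 0.5 | 0.11 | 0.10 |
| 1 | 0.22 | 0.20 |
| 2 | 0.45 | 0.39 |
| 3 | 0.67 | 0.59 |

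**Step 6: chance imbalance.** With independent Binomial(n, p) numbers of users in two arms, the probability that they differ by at least two is:

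| p | n = 10 | n = 13 |
|---|---|---|
| 1% | 0.8% | 1.3% |
| 2% | 2.7% | 4.2% |
| 5% | 11% | 16% |
| 10% | 24% | 31% |
| 20% | 39% | 46% |

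A difference of exactly two users moves the contrast by 2k/√(2n), which at k = 1 is 0.45 SE (n = 10) or 0.39 SE (n = 13). The rate p stands for one exposure at a time. Post-dosing supplements and pre-enrolment antibiotics would have different rates. Nothing in the Protocol supports 10% or 20% for new supplement use within 6 to 13 days.

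**Step 7: average loss of precision.** A fraction p of users, each shifted by k SD, multiplies the variance by 1 + p(1 − p)k². At p = 1%, k = 1 this is 1.0099, so the SE rises by 0.5%. At p = 5%, k = 1 it is 1.0475, a rise of 2.3%. At p = 5%, k = 3 it is 1.4275, a rise of about 19%.

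**The case against.** The strongest reply is that nothing here is wrong or contradictory. Tying the supplement rule to the dosing period protects the exposure contrast while capsules are taken and keeps the burden on participants low. The antibiotic part can be read as a wish for one more criterion: exclusion item 9 is open-ended about recent illness and will catch many recent courses, and the Day 3 fecal sample allows each person's change to be examined. The fatty-acid samples on Days 6 and 13, which carry the on-supplement evidence, lie inside the restriction. Every figure for size rests on assumed rates and shifts.

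Most of this stands, and it is why the point is minor. Two parts do not fully answer it. The Day 3 sample records a starting level but does not remove continuing recovery after a recent course, and the Protocol does not say whether it precedes the first capsule in the arm that starts that day. Item 9 stops at one month, whereas item 4 shows that the authors thought three months appropriate for products acting on the flora.

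A reader might infer that the antibody comparison is biased because antibodies are sampled to Day 26 without a supplement rule. The Protocol does not support that: groups are randomised, and participants, implementers and analysts are blinded, so there is no stated reason for use to differ systematically by arm. Nor does it support reading the fatty-acid outcome as compromised throughout.

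**Conclusion.** The point holds as a minor, inexpensive improvement. Two rules fall short of the secondary mechanism outcomes: the gut-flora screen leaves out antibiotics, and the supplement limit stops, by inference, at Day 13, up to 6 days before the last fatty-acid sample and up to 13 days before the last fecal sample. The expected consequence is extra noise and chance imbalance in arms of 10 to 13, not bias in the primary comparison. Its size cannot be fixed from the Protocol. If use is rare or shifts are small it is negligible: about 0.2 SE for one user shifted by 1 SD. It becomes noticeable only under higher assumed use or large shifts. The conclusion rests on the inferred date of the second dose and on the blinding working as described. The sample size is unaffected.

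**What to change.** Adopt these four changes together:

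1. Add antibiotics to exclusion item 4, with the same three-month look-back.
2. Ask participants to avoid other nutritional supplements, naming probiotics and prebiotics, until the last sample on Day 26.
3. Record any supplement or antibiotic use, with dates, at the visits already scheduled. Clinically needed treatment is always given.
4. Move supplement use out of the Drop out list. Treat it as a recorded deviation with continued follow-up and inclusion in the primary analysis.

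Change 2 should not be made without change 4. Supplement use is now a drop-out criterion, so a longer window on its own would remove more participants after randomisation from small arms, which could do more harm than the noise it prevents.

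The cost is a few lines of text and a short use record. The downsides are a few more screening failures, 26 − 13 = 13 more days of restriction, and slight dilution of the contrast from users who are now retained.

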### Masking:

The three-blind design was adopted, and the study implementers, research subjects, data monitoring and statistical analysts were blinded.

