##### **Follow-up indicators:**

###### **1) Primary indicators:**

- ① Rabies virus antibody titers: to examine the specific antibody after intervention.

Will be tested on day 6, 13, 16, 19 and 26.

- ② Neutralizing antibody: to test the ability of binding to rabies virus

Will be tested on day 6, 13, 16, 19 and 26.

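### The Drop out list treats non-adherence and other supplement use as drop-out and does not keep these participants under scheduled sampling

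*Protocol*

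**What the plan says.** Section 4.1 of the protocol has one undivided list of five events under the heading Drop out. Item 1 is "Use of other nutritional supplements during the intervention" and item 2 is "Those who do not consume nutritional supplements as prescribed by the doctor". Major illness, severe vaccine allergy and voluntary withdrawal follow. No consequence is attached to any item: the list does not say whether the person stops capsules, leaves the study or is left out of the analysis.

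On timing, section 4.3 says that "nutritional supplement intervention was performed 3 days before the first dose of vaccine to the second dose of vaccination". Both primary antibody measures carry the same schedule: "Will be tested on day 6, 13, 16, 19 and 26". The safety indicators put glucose and lipids on Days 3 and 13, the GAD-7 on Day 13 and the blood count on Days 3 and 26.

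Section 4.2 arrives at 10 per group and, "setting the expected loss of follow-up rate at 20" per cent, recruits 13. It does not say whether people dropped under items 1 and 2 count towards that allowance.

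**The concern.** Items 1 and 2 are departures from the assigned intervention. Voluntary withdrawal is an exit from the study. When both stand under one heading whose ordinary meaning is leaving, site staff can reasonably stop drawing blood from a participant who misses capsules or takes another supplement.

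That would select participants on something that happens after randomization. The arms are comparable as randomized. They need not stay comparable once people are removed for how they behaved on their capsules. If removal is related to both arm and antibody response, the comparison serving objective 1 is biased. Objective 2 suffers too: the trial records gastrointestinal discomfort as an adverse reaction, and someone who stops capsules for that reason would be missing from the later safety tests.

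This cannot be left to the statistical analysis plan. That plan can define analysis sets, but it cannot recover samples that were never drawn. Who continues to be sampled is a conduct rule and belongs in the protocol.

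**Working it through.** **Which visits are at stake**

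- First dose: the sample collection list equates trial Day 6 with vaccination Day 0.
- Second dose: the Background gives a 0, 7, 21-day schedule, so the second dose falls on trial Day 6 + 7 = 13. The sample list likewise equates Day 13 with vaccination Day 7.
- Supplementation ends at the second dose (section 4.3), so items 1 and 2 can apply up to about Day 13.
- Day 6 is vaccination Day 0 in people not previously vaccinated (inclusion criterion 3), so that sample serves as a baseline. Four of the five antibody tests follow vaccination: Days 13, 16, 19 and 26.

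Assessments lost if sampling stops at removal:

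| Removed | Antibody tests lost | Safety tests lost |
|---|---|---|
| At Day 13, after that day's assessments | Days 16, 19, 26 | Day 26 blood count |
| After Day 6, before Day 13 | Days 13, 16, 19, 26 | Day 13 glucose, lipids, GAD-7; Day 26 blood count |
| Before Day 6 | All of these and the Day 6 baseline | As in the row above |

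One removal out of 13 is 1/13 = 7.7% of an arm.

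**The plan's own sample size reproduces**

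Inputs from section 4.2: means 1323 and 164.8, SDs 1093.9 and 123.4, two-sided alpha 0.05, power 0.90, loss 20%.

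- Difference: 1323 − 164.8 = 1158.2.
- Pooled SD with equal groups: √((1093.9² + 123.4²)/2) = 778.4.
- N = 2 × ((1.960 + 1.282)/1158.2)² × 778.4² = 9.49, rounded up to 10.
- 10/0.8 = 12.5, rounded up to 13.

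These figures are not in dispute.

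**What retaining non-adherent participants costs**

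The protocol gives no non-adherence rate, so 20% and 10% are assumptions. Suppose a fraction p of ARA participants gain nothing. The expected difference becomes (1 − p) × 1158.2: 926.6 at 20% and 1042.4 at 10%. Power is for a two-sided t-test at 0.05 with 13 evaluated per arm, under three assumptions about the SD:

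- A: SD stays at 778.4.
- B: the ARA variance grows by the mixing term, 778.4² + p(1 − p) × 1158.2², and is pooled with 778.4². The SD is 844.5 at 20% and 816.3 at 10%.
- C: non-gaining participants have the control mean and the control SD of 123.4, and the others have the ARA SD of 1093.9. The pooled SD is 771.4 at 20% and 779.2 at 10%.

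| Assumed p | A | B | C |
|---|---|---|---|
| 20% | 0.829 | 0.765 | 0.836 |
| 10% | 0.906 | 0.878 | 0.905 |

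The comparator is 10 adherent participants per arm with no dilution (1158.2, SD 778.4): t-test power 0.882. The plan's normal-approximation formula gives 0.914 for the same case.

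**Size of any bias**

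This would need the removal rate in each arm and the association of removal with antibody response. The protocol gives neither, so no figure is offered.

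**The case against.** The strongest reply is that the harm is inferred. The list attaches no consequence to any item, and the sampling schedules are not made conditional on adherence. Drop out might mean only exclusion from an analysis set, which the statistical analysis plan (not shown) would define. This stands in part. A reader might infer that the protocol orders sampling to stop; it does not say so. What remains is that the ordinary meaning of the heading is leaving, that the two items share a list with voluntary withdrawal, and that nothing says sampling goes on.

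A reader might also infer that the comparison is biased, or that removal will differ between arms. The documents do not support either. Capsule number is the same (the placebo group takes six "500 mg sunflower oil capsules each day", and the ARA groups take six capsules of the same size), and under Masking "the study implementers, research subjects, data monitoring and statistical analysts were blinded". Capsule contents differ, so differential removal is possible, but nothing shows that it happens.

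The intervention periods also differ by design: "The second group will receive nutritional supplements 500mg/day, starting on days 6 of the study", which gives 7 days up to Day 13, against 10 days from a Day 3 start. This adds little. The Day 3 ARA and placebo groups both start on Day 3, so that comparison is untouched. For the Day 6 group, the protocol does not say whether other capsules are taken before Day 6.

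It is also fair that no visit lies between Day 6 and Day 13. If non-adherence comes to light at the Day 13 visit, that day's samples may still be drawn, and the loss is then the first row of the visit table.

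**Conclusion.** The point holds as a poorly fixed conduct rule that should be corrected before recruitment. What is certain is the wording: two departures from the intervention are classed as drop-out, and continued sampling is not provided for. What is conditional is the harm. If the rule is followed in its ordinary sense, each affected participant loses three or four of the four post-vaccination antibody tests and the later safety tests. Bias in the primary comparison requires, in addition, that removal be related to both arm and response. If removal is unrelated to response, the cost is lost participants and no bias.

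A reader might take the dilution figures to mean that 13 per group is too few. They do not establish that. They rest on assumed non-adherence rates, and a further inflation for 20% loss would count some of the same people twice, because the fix keeps them in. The gain from the change is less risk of bias and more complete safety data, not more power.

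**What to change.** Reword the Drop out list in section 4.1 so that items 1 and 2 are recorded as protocol deviations and are not reasons to leave the study. State that the samples and safety assessments already scheduled continue to Day 26 for every randomized participant who still consents, so that all can be analysed in the assigned arm. No change to any clinical rule is proposed.

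The change is to wording only, and no visit is added. The price is the dilution of the estimated effect shown above, which the sponsor should accept knowingly. Reporting how many participants met items 1 and 2 in each arm would let readers judge it.
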